8.8.5 Harris Hip Score at Pre-Op, 6 week, 24 week

Harris hip scores are assessed at the Pre-Op visit and at 6 week and 24 week. Results within each visit window will be summarized and changes from baseline will be provided using the Per Protocol Analysis Set. Standard continuous summaries will be supplemented with 95% confidence intervals using the t distribution.

8.8.6 Forgotten Joint Score (FJS-12) at 6 week, and 24 week

FJS-12 scores are assessed at 6 week, 24 week. Results within each visit window will be summarized and the change at 24 week from 6 week will be provided using the Per Protocol Analysis Set. Standard continuous summaries will be supplemented with 95% confidence intervals using the t distribution.

8.8.7 EQ-5D-5L at Pre-op, Week 6, and Week24

The EQ-5D-5L US index values and EQ-VAS values are assessed at Pre-op, 6 week, and at 24 week. Results within each visit window will be summarized and the change from Pre-op will be provided using the Per Protocol Analysis Set. Standard continuous summaries will be supplemented with 95% confidence intervals using the t distribution.

8.8.8 Hip Evaluation at Pre-op, 6 week, 24 week

All questions on the Pre-op hip evaluation CRF will be summarized: ("How satisfied do you anticipate you will be with this procedure?", "Groin pain", "Buttock pain", "Leg length", "Can you walk without an aid?", "Do you drive?", "Can you perform basic activities of daily living (bathing, getting in and out of bed, etc)?", "Can you perform light household duties? (cooking, dusting, etc.)", "Can you perform moderate/heavy household duties (cleaning floors, moving heavy boxes, etc.)?", "Can you go up and down a flight of stairs using a handrail?", "Can you put on socks/stockings without someone's assistance?", "Can you bend down to pick up an object on the floor?", "Can you stand up from a chair without assistance?", "Con you work?") as categorical data using the Per Protocol Analysis Set.

All questions on the Post-op hip evaluation CRF will be summarized: "How satisfied are you with this procedure?", "Would you have this procedure again?", "Groin pain", "Buttock pain", "Leg length", "How long did you take narcotics after your surgery?") as categorical data using the Per Protocol Analysis Set.

8.8.9 Hip Evaluation Functional Recovery Outcomes

All questions on the hip evaluation functional recovery outcomes will be summarized as categorical data using the Per Protocol Analysis Set in the following fashion: recovery time will be the first week (Week 1 – After Week 12) recovery was achieved; Otherwise, recovery time will be "Still cannot do" or "Not Applicable/I never do this" if subject selected these options at the last visit subject was seen.

8.8.10 Radiographic Outcomes (based upon: AP Hip, AP Pelvis, and Lateral) at week 6, week 24

The following radiographic endpoints will be summarized at week 6 and at week 24: Acetabular cup version – Hip, Acetabular cup version – Pervis, Acetabular cup Inclination, Acetabular cup migration, Acetabular cup radiolucency, Acetabular cup osteolysis, Acetabular cup scerotic lines, Acetabular cup porous coating integrity, Femoral stem position, Femoral stem tilt, Femoral stem subsidence, Femoral stem radiolucency, Femoral stem osteolysis, Femoral stem osteolytic lines, Femoral stem coating integrity, Calcar resorption, Calcar fracture, Heterotopic ossification, Proximal femur, Pelvis vertical alignment, Device/anatomy condition.

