7.3 Six Week Postoperative Evaluation (Day 14 – Day 60)

The following data will be collected from six-week postoperative evaluation:

- Study Visit (CRF detailing type of visit and subject status)
- Postoperative Hip Evaluation (HE2)
- Postoperative Hip Evaluation Functional Outcomes (HE3*)
- Narcotic Drug Use (patient reported)
- Harris Hip Score
- Radiographs (AP Hip (unilateral), AP Pelvis (bilateral), and Lateral)
- EQ-5D-5L
- Forgotten Joint Score
- Adverse Event Form (if needed)
- Protocol Deviation Form (if needed)
- Device Deficiency (if needed)
- End of Study (Withdrawal) Case Report Form (if needed)

* The Functional Outcomes portion of the Hip Evaluation CRF (HE3) will be initially completed at the 6 week visit, and only questions that are marked as "still cannot do" or "still have not returned to work" will be addressed at subsequent study visits

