7.4 Twenty-Four Week Postoperative Evaluation (Day 61 to Day 200)

The following data will be collected from twelve-week postoperative evaluation:

- Study Visit (CRF detailing type of visit and subject status)
- Postoperative Hip Evaluation (HE2)
- Postoperative Hip Evaluation Functional Outcomes (HE3*)
- Narcotic Drug Use (patient reported)
- Harris Hip Score
- Radiographs (AP Hip (unilateral), AP Pelvis (bilateral), and Lateral)

EQ-5D-5L

Confidential Version Date: 040CT2021 DePuy Synthes Protocol DSJ_2019_03 / Version 2.0 / TV-eFRM-02920

- Forgotten Joint Score
- Adverse Event Form (if needed)
- Protocol Deviation Form (if needed)
- Device Deficiency (if needed)
- End of Study (Withdrawal) Case Report Form (required unless completed previously)

* The Functional Outcomes portion of the Hip Evaluation CRF (HE3) will be initially completed at the 6 week visit, and only questions that are marked as "still cannot do" or "still have not returned to work" will be addressed at subsequent study visits

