With no prospectively planned hypotheses, the following secondary endpoints will be summarized at all visits with available data for both treatments as categorical variables:

- Post-op time when functional activities can be accomplished (return to work; self-care; etc.)
- Narcotic drug usage throughout the study (patient reported)

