The following analysis sets are defined:

- Enrolled The Enrolled population set will consist of all subjects who sign the informed consent document.
- Safety The Safety population set will consist of all subjects in the Enrolled population set for whom treatment was attempted, according to the actual treatment received.
- Per Protocol The Per Protocol population set will consist of all subjects in the Enrolled population set who successfully received the planned treatment, who met all inclusion/exclusion criteria, who were seen at least once at a post-operative visit, and who did not have any protocol deviations which were prospectively determined to potentially have influence on the scientific validity of the data (such as inclusion/exclusion criteria).

7 Sample Size Justification

Primary endpoint Non-Inferiority (NI) analysis: Based upon input from key opinion leaders (KOLs) and data from other studies, typical femoral broaching time with manual instruments is anticipated to have a range of 5 to 15 minutes, which implies a standard deviation of approximately 2.5 minutes (1/4 of the range). Moreover, KOLs suggest that a difference of 10 minutes in femoral broaching time (increase for a single patient) is clinically meaningful. The non-inferiority margin of 1.25 minutes was established because it Page 8 of 29

is ½ of the anticipated standard deviation and is much less than a clinically meaningful difference. Under a 1-sided test with 5% alpha, a sample size of N=88 per group would be sufficient to demonstrate non-inferiority with 95% power. A sample of size N=200 per group (N=400 total) was chosen as feasible by the sponsor and desirable for providing further data for both KINCISE and Anterior Advantage; this sample size would provide more than 99% power to demonstrate non-inferiority for the primary endpoint analysis.

Primary endpoint supplemental superiority analysis: It is not known if there will be a true difference in means between groups. However, if there is a true difference of 1 minute between group means (lower time favoring KINCISE), and assuming an SD as stated above (2.5 minutes), then a sample of N=200 per group (N=400 total) would provide approximately 99% power to demonstrate superiority.

Secondary endpoint analyses:

• Non-inferiority of skin-to-skin OR time

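### SAP 8.8.9 pools 'Still cannot do' answers given anywhere from day 14 to day 200 in one category of a time-to-recovery endpoint, an unlisted departure from the protocol's by-visit summary

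*SAP*

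**What the plan says.** The endpoint is the time after surgery at which everyday activities, including work and self-care, can be resumed. Protocol 4.2 and 10.5.2 list it among the secondary endpoints without hypotheses.

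- **Collection.** Protocol 7.3: "The Functional Outcomes portion of the Hip Evaluation CRF (HE3) will be initially completed at the 6 week visit". Only items still unrecovered then (including not yet back at work) are asked again at later visits.
- **Analysis rule.** SAP 8.8.9 gives one value per subject and item: "recovery time will be the first week (Week 1 – After Week 12) recovery was achieved". Otherwise the value is 'Still cannot do', or the not-applicable answer, "if subject selected these options at the last visit subject was seen". The rule sets no minimum follow-up and requires no 24-week visit.
- **Windows.** Protocol 7.3 and 7.4 and SAP section 4 set the 6-week window at day 14 to 60 and the 24-week window at day 61 to 200.
- **Analysis set.** SAP 8.8.9 uses the Per Protocol set, which SAP section 6 limits, among other conditions, to subjects "who were seen at least once at a post-operative visit".
- **Protocol display.** Protocol 10.9.4 has this endpoint summarized as a categorical variable at every visit that has data.
- **Missing data.** SAP 8.11 plans no imputation and SAP 8.13 no sensitivity analyses.

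**The concern.** An unrecovered answer at a visit says only that recovery had not happened by that day. Its meaning depends on when the visit took place. SAP 8.8.9 drops the day and keeps the answer, so one row mixes subjects observed for two weeks with subjects observed for more than six months.

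A reader of the table will naturally take that row as the share who had not recovered by the end of the study. For anyone whose last visit was early, that is not known. Subjects lost or withdrawn after the 6-week visit are affected, including those withdrawn for cup or stem revision under protocol 3.5.5. So are attenders whose final visit falls early in the wide 24-week window. At stake is whether a named secondary endpoint is described accurately. No test or success criterion depends on it.

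**Working it through.** The plan states no rate or sample size for this endpoint, so there is no figure to reproduce. The check sets the rule against the visit windows.

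**1. Spread of follow-up behind one category.** Weeks = day / 7.
- Earliest possible last visit: 14 / 7 = week 2.0. Latest: 200 / 7 = week 28.6. Spread: 200 − 14 = 186 days.
- Within the 24-week window alone: 61 / 7 = week 8.7 to week 28.6. Spread: 200 − 61 = 139 days.

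**2. Who is included.** One post-operative visit can satisfy the follow-up condition of the Per Protocol set. A subject seen only at 6 weeks can therefore be in the table, with the 6-week answer as the only recorded outcome.

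**3. What a final visit on day 61 to 84 can and cannot record.** Week 12 ends on day 12 × 7 = 84, so 'After Week 12' cannot be reported at a visit on or before that day. Take a subject who recovers in week 14 (days 92 to 98):
- last visit on day 70 (week 10): recorded as 'Still cannot do';
- last visit on day 150 (week 21.4): recorded as 'After Week 12'.

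A subject who recovered in week 8 is recorded in week 8 at either visit. Only those still unrecovered at the early final visit are affected.

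**4. Direction.** The rule counts first recovery. Further follow-up can move a subject out of 'Still cannot do' but never into it from a recovery week. Compared with following everyone to day 200, the row can therefore only be too large or equal.

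**5. Protocol against SAP.** Protocol 10.9.4 planned a summary at each visit; SAP 8.8.9 gives one value across visits. SAP Table 10.1 lists two substantive changes, the removal of thigh pain and the correction of 'alternative' to 'null', and not this one. SAP 8.8.5 to 8.8.7 summarize the Harris, Forgotten Joint and EQ-5D-5L scores within each visit window. SAP 8.8.9 also does not mention the not-returned-to-work answer, although return to work is part of the endpoint.

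**6. Illustration of size (all inputs assumed).** Let d be the share with no 24-week visit, p6 the share unable at 6 weeks and p24 the share unable at 24 weeks. Suppose those who miss the visit recover like the rest. Then

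recorded share = d × p6 + (1 − d) × p24, and excess = d × (p6 − p24).

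For example, 0.10 × 40% + 0.90 × 5% = 8.5%, an excess of 3.5 points.

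| p6 / p24 | d = 2% | d = 5% | d = 10% | d = 15% |
|---|---|---|---|---|
| 20% / 5% | 5.3% (+0.3) | 5.75% (+0.75) | 6.5% (+1.5) | 7.25% (+2.25) |
| 40% / 5% | 5.7% (+0.7) | 6.75% (+1.75) | 8.5% (+3.5) | 10.25% (+5.25) |
| 60% / 10% | 11.0% (+1.0) | 12.5% (+2.5) | 15.0% (+5.0) | 17.5% (+7.5) |

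This covers only missed 24-week visits. The effect of early visits within the 24-week window is extra, and the documents give no distribution of visit days from which to gauge it.

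**The case against.** The strongest reply is that little hangs on this row. The endpoint is descriptive and outside the gatekeeping sequence, and study success rests on broaching time alone. Protocol 3.5.6 expects loss to follow-up to be infrequent; with 2% missing, the illustration gives at most 1.0 point. The SAP never calls the category a failure or a 24-week status. It is the subject's own answer when last seen, and it is true as such. SAP 8.2 also reports deaths, revisions and the follow-up rate by interval. All of this stands and limits the weight of the point. It does not remove it: the row carries no follow-up time, and the SAP 8.2 accounting uses the Safety set and does not list the functional-recovery form among its endpoints.

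Four stronger readings are tempting, and the documents do not support them.

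- **Anyone closed out on day 61 to 84 must be 'Still cannot do'.** Recovery in any week already past is recorded normally, as step 3 shows.
- **Many final visits will fall that early.** Days 61 to 84 are 24 of the window's 140 days, but that counts calendar days, not visits. Protocol 7.4 does say "The following data will be collected from twelve-week postoperative evaluation", yet it does so under a 24-week heading and the visit is called 24-week elsewhere, so this is probably a slip.
- **The rule will create a difference between arms.** That needs visit timing or dropout to differ by arm. The rule and windows are the same in both arms, and SAP section 3 randomizes 1:1 in blocks of 4 within each site's own sequence, which tends to balance site visit habits. The lack of blinding after assignment makes a difference possible, but nothing in the documents shows one.
- **Ordinary Kaplan-Meier estimates to week 24 would settle it.** 'After Week 12' is open-ended and has no event week, so that curve cannot be drawn without inventing dates.

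**Conclusion.** The point holds as a reporting weakness. SAP 8.8.9 pools unrecovered answers from day 14 to day 200 in one category, counts subjects with only a 6-week visit beside those followed to week 24, and departs from protocol 10.9.4 without listing the change. The direction follows from the rule itself: read as status at the end of follow-up, the row tends to overstate non-recovery. The size cannot be derived, because the documents give no rates of dropout or recovery and no visit-day distribution. The illustrated excess runs from 0.3 to 7.5 points and rests wholly on assumed inputs, including that subjects who miss the 24-week visit would recover like the rest. That is doubtful for those withdrawn for revision. The primary and the three hypothesis-tested secondary analyses are untouched. It is worth correcting before analysis because the correction is cheap.

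**What to change.** Revise SAP 8.8.9 as follows.

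1. Report each HE3 item cumulatively at the 6-week and 24-week visits, with the number assessed at each, in line with protocol 10.9.4. Recovered items are not asked again, so the 24-week column must carry forward recoveries already reported at 6 weeks. Its denominator should be the subjects with a 24-week-window visit, whether recovered or not.
2. If a single-value table is kept, take 'Still cannot do' and the not-returned-to-work answer only from a 24-week-window visit. Put unrecovered subjects without that visit in a separate row, such as 'not recovered when last seen (no 24-week visit)', and summarize the day of the last visit. List this table in SAP Table 10.1.
3. Any optional time-to-recovery summary should treat 'After Week 12' as interval-censored between week 12 and the visit date. It should show subjects withdrawn for revision separately rather than assume that their censoring is non-informative.

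The cost is SAP wording and a slightly longer table. The data are already collected, and there is no added burden on sites or subjects.

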8.8.11 Narcotic Drug Usage

A listing of narcotic drug use will be provided using the Safety population set which will include: treatment group, subject id, time point, name of medication, 24 hour dose, dose, and whether drug usage is ongoing.

8.9 Safety Analyses

Adverse Events (AE) will be coded according to the Medical Dictionary for Regulatory Activities (MedDRA) version 22.0. Analyses will be conducted for all subjects in the Safety Analysis Set.

All AEs from the start of device placement until subject finishes participation in the study will be summarized by treatment group and combined with frequencies, number of subjects with at least one AE, and percentages for the following categories:

- Overall
- Device related (AE marked Possible, Probable, or Causal Relationship by investigator)
- Procedure related (AE marked Possible, Probable, or Causal Relationship by investigator)
- Serious (SAE)
 - \circ led to death

The number (%) of subjects with adverse events will be presented by MedDRA system organ class (SOC) and preferred term (PT) for all AEs, and for all SAEs separately for each treatment group and combined. In these summaries, AEs will be sorted by decreasing frequency within each MedDRA SOC and PT in the combined cohort. A subject-level listing will be provided to display details of all reported AEs.

A listing of device deficiencies will also be provided.

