7.5 Study Completion

A study completion CRF should be completed for each subject for the following reasons (list may not be inclusive of all reasons for study withdrawal):

- 1) Subject withdraws consent
- 2) Subject has the cup and/or stem revised or removed
- 3) All data is entered onto the CRFs as completely as possible and the Subject completes study per protocol
- 4) Subject dies
- 5) Subject is lost to follow up
- 6) Subject is a screen failure after consenting as described in section 3.5
- 7) Subject is withdrawn by the Investigator

8 Adverse Events (AEs)

An adverse event (AE) is defined as an untoward medical occurrence, unintended disease or injury, or untoward clinical signs (or change or worsening of a pre-existing medical condition) in a patient, which may or may not have an association with the device. In addition, an adverse device effect is defined as "any untoward and unintended response to a medical device". Further types of AEs and definitions are located in **Table 8-1** below.

For this study, there are three types of events that will need to be reported via the Adverse Events (AE) eCRF:

1) Device Related AEs (see Section 8.3 and Figure 8-1 below)

Confidential Version Date: 04OCT2021

DePuy Synthes Protocol DSJ_2019_03 / Version 2.0 / TV-eFRM-02920 Page **25** of **53**

- 2) Procedure Related AEs (see Section 8.4 and Figure 8-1 below)
- 3) Serious AEs (See Table 8-1 and Figure 8-1 below)

A record of each reportable adverse event, including details of the nature, onset, duration, severity, seriousness, relationship to the device, relationship to the operative procedure and outcome, will be made on an Adverse Events eCRF. Subjects must be questioned about any adverse event(s) at each subsequent encounter, whether a protocol scheduled follow up visit or not. The date that the site first became aware of the Subject's adverse event will also be documented (i.e., "site awareness date"). "Site awareness" is defined as the time when medical personnel and/or the site's study team, who are employed by or otherwise formally affiliated with the site (i.e., clinic and/or the hospital entity utilizing the same EMR system), obtain information about a reportable event.

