8.3 Device or Procedure Related

The determination whether the AE is related to the device or procedure will be based upon whether a causal relationship between the device or procedure and the AE is at least a reasonable possibility, *i.e.* the relationship cannot be ruled out. A causal relationship cannot be ruled out if, in the medical judgment of the Investigator, the effect follows a reasonable temporal association with the use of the device and/or is confirmed by the improvement of the effect upon discontinuation of the clinical use of the device, and/or the effect is not reasonably explained by the Subject's clinical state.

Relationship to study device or procedure should both be rated as follows, "*Is this event related to the study device (or procedure)?*" options are: Definitely, Probably, Possibly, Remote possibility or Definitely not. All adverse events (medical change from baseline) experienced by a subject should be noted in their source documents with these relationships to document the sites' determination.

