10.9.5 Safety Analyses

All safety analyses will be performed on the Safety Population set.

All Adverse Events (AE) from the start of device placement until subject finishes participation in the study will be summarized with frequencies, number of subjects with at least one AE, and percentages for the following categories: Overall, SAE, death, device and procedure related. AEs will also be summarized by Preferred Term within System Organ Class for overall for all reported AEs as well as for the subset of SAEs.

Re-hospitalizations during the study within 90 days post-op and complications within 90 days post-op will be summarized.

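### SAP 8.9 defines related adverse events with a label that is not on the protocol's rating scale, omits the scale's strongest rating, and gives no mapping between the two

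*SAP*

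**What the plan says.** Protocol section 8.3 sets one scale for relationship to the device and to the procedure. The "options are: Definitely, Probably, Possibly, Remote possibility or Definitely not". The same section says that relatedness depends on whether "a causal relationship between the device or procedure and the AE is at least a reasonable possibility", and explains this as meaning that "the relationship cannot be ruled out".

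Protocol section 8 says that a record of, among other details, "relationship to the device, relationship to the operative procedure and outcome, will be made on an Adverse Events eCRF". The form itself is not part of the documents.

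For the analysis, Protocol section 10.9.5 asks for "percentages for the following categories: Overall, SAE, death, device and procedure related", but does not say which ratings count as related. SAP section 8.9 does say: for the device row and again for the procedure row, an event counts if it is an "AE marked Possible, Probable, or Causal Relationship by investigator".

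SAP section 10 (Table 10.1) lists two substantive changes from the protocol: the removal of thigh pain, and the replacement of one word in the rule for sequential testing. It does not mention the relatedness scale.

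**The concern.** SAP 8.9 is the only place in either document that turns investigator ratings into a related or not-related count. It does so in labels that do not match the scale on which the ratings are made. One of its three labels has no counterpart on that scale, and the scale's strongest rating has no counterpart in the rule.

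Two safety rows, each by arm and combined, depend on this line. They matter here because the protocol makes relatedness part of what is collected: section 8 names device-related, procedure-related and serious events as the three types to report. If the rule is programmed without resolving the labels, the events that investigators attribute most firmly to the device or procedure would be missing from the rows meant to show them. SAP 8.13 plans no sensitivity analysis, so no other summary would show the effect of the choice.

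The lowest rating short of a denial, *Remote possibility*, raises a second question. The SAP leaves it out without comment, and the protocol's test can be read either way.

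**Working it through.** No power, alpha or sample-size figure bears on this, and the plan states no figure to reproduce. The check is a comparison of labels.

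| Protocol 8.3 rating | Label in SAP 8.9 | Result |
|---|---|---|
| Definitely | none | no match |
| Probably | Probable | same term, different word form |
| Possibly | Possible | same term, different word form |
| Remote possibility | none | not counted as related |
| Definitely not | none | not counted as related, as expected |
| (no such rating) | Causal Relationship | no counterpart on the scale |

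Step 1. The word-form differences in the second and third rows are immaterial. The real mismatch is *Causal Relationship* against *Definitely*.

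Step 2. Look for a mapping elsewhere. Protocol 10.9.5 names the categories but not the ratings behind them, and SAP Table 10.1 is silent. There is none.

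Step 3. Effect on the count. Let R be the number of events rated *Definitely*, *Probably* or *Possibly*, and D the number of those rated *Definitely*. Write d = D / R.

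- With *Causal Relationship* mapped to *Definitely*: count = R, shortfall = 0.
- Without the mapping: count = R − D = R(1 − d), a shortfall of d.

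The documents give no value for d. As an assumption only, take d from 10% to 50%. For every 100 related events, the unmapped rule would then count 100 − 10 = 90 down to 100 − 50 = 50. The number of subjects with at least one related event falls only for subjects whose related events are all rated *Definitely*, so that figure can fall by less.

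Step 4. *Remote possibility*. Protocol 8.3 gives a test and an explanation of it. Under the test, a reasonable possibility, a remote one can be held to fall short. Under the explanation, a relationship that cannot be ruled out, it can be held to qualify, because the scale has a separate rating for denial. Neither document assigns this rating to related or unrelated.

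Step 5. What depends on the definition. Only the device-related and procedure-related rows use it. The overall AE count, the SAE and death rows, the summaries by system organ class and preferred term, the AE listing and all hypothesis tests do not.

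**The case against.** The strongest reply is that the undercount needs an unlikely reading. The SAP's three labels ascend, and the third stands where *Definitely* stands on the protocol scale. A rule that keeps the two weaker ratings and drops the strongest makes no sense, and a programmer would probably see that. A strictly literal match would also reject *Probably* and *Possibly*, leaving both rows empty, and that error would be noticed at once. The AE form is not in the documents either; if it carries the SAP's labels, no event is lost.

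Most of this stands. A reader might infer that the rule will in fact drop the *Definitely* events. The documents do not support that. They show a rule that does not fit its scale, and the loss is a risk that depends on how the rule is applied. Some caution about relying on good sense is still fair: SAP 8.2 counts RSA subsidence, HOOS Jr. and linear head penetration, none of which is in the protocol's Time and Events Table. It is therefore unsafe to assume that the SAP's labels were checked against this study's forms. If the form does use the SAP's labels, it departs from Protocol 8.3 and the two still need reconciling.

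A reader might also infer that Protocol 8.3 requires *Remote possibility* to be counted as related. It does not clearly do so. The operative test is a reasonable possibility, and the phrase about ruling out explains that test and is tied to the investigator's medical judgment. Leaving the rating out may agree with the protocol.

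Nor is the silence of Table 10.1 a contradiction in itself. The table covers substantive changes only, and Protocol 10.9.5 contains no rating rule for the SAP to have changed.

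Finally, the reply notes that the consequences are contained. Because reporting is limited largely to related or serious events, any *Definitely* event missing from a related row would still be in the overall AE count and in the listing. That is correct.

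**Conclusion.** The point holds as a mismatch between a stated analysis rule and the scale it is applied to. SAP 8.9 uses a label that investigators cannot give under Protocol 8.3, omits the strongest one they can give, and supplies no mapping. Whether any event is lost depends on the implementation: none if *Causal Relationship* is read as *Definitely*, and all *Definitely* events in both related rows if it is not. No count can be put on this from the documents, and nothing in them shows whether a shortfall would differ between arms.

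On *Remote possibility* the finding is an ambiguity to be settled in writing. It is not a breach of the protocol.

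The trial's success criterion and every hypothesis test are untouched. The correction is worth making because these rows have no other operational definition and the change is very small. The conclusion rests on Protocol 8.3 as the governing scale, since the form itself could not be examined.

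**What to change.** In SAP 8.9, replace the parenthetical definition in both the device-related and the procedure-related rows with the protocol's own labels, so that *Definitely*, *Probably* and *Possibly* count as related. Show *Remote possibility* as a separate row, so that the related-AE figures can be read with and without it and neither reading of Protocol 8.3 has to be imposed. When making the edit, check the response options on the AE eCRF and reconcile them with Protocol 8.3 if they differ.

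The cost is one line of SAP wording and one extra table row. No other analysis changes.
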